4. Able to come to the VA CRC for study visits over 4-9 weeks (necessary if the subject is randomized to the weight loss intervention group)
5. Patient agrees to stop taking dietary or vitamin supplements (Lycopene***, Vitamin E, selenium, genistein, fish oil) or herbal supplements (e.g., saw palmetto, PC-SPES) prior to starting the dietary intervention.

Exclusion Criteria:

1. Gleason grade of prostate cancer > 4+5.
2. History of ever receiving androgen deprivation therapy or antiandrogen therapy
3. History of receiving finasteride* in the past 9 months
4. Patient receiving insulin** for diabetes mellitus
5. Current use of weight loss medications
6. Significant co-morbidities (i.e. cardiac, pulmonary, liver disease, ongoing alcohol/drug abuse)
7. Cardiac pacemaker

* Androgen deprivation therapy: Leuprolide, Goserelin. Antiandrogen therapy: Flutamide, Bicalutamide

** Changes in insulin levels may impact on the proposed biomarkers (IGF-1, IGFBP-1)

*** Lycopene has previously been shown to impact on apoptosis in prostate cancer tissue⁶⁴

Clinical Trial Flow Chart:

Activity	Screen											surgery
	wk -1 to 0	baseline	wk 1	wk 2	wk 3	wk 4	wk 5	wk 6	wk 7	wk 8	wk 9	
	V1	V2	V3	V4	V5	V6	V7	V8	V9	V10	V11	
Obtain Informed Consent	✓											
Review Inclusion/Exclusion	✓											
Medical Hx & Phys Exam	✓											
Concomitant Medications	✓ 		✓	✓	✓	✓	✓	✓	✓	✓	✓	
Waist-to-Hip measurement ³	✓	✓		✓		✓						✓
Weight	✓	✓	✓	✓	✓	✓	✓	✓	✓	✓	✓	
Give subject 3-Day Food Diary to complete		✓	✓	✓	✓	✓	✓	✓	✓	✓		
Randomization	✓											
DEXA Scan	✓											✓
Collect 3-Day Food Diary		✓	✓	✓	✓	✓	✓	✓	✓	✓	✓	
Serum Biomarkers/Bioassays ¹	✓											✓
Weight loss Intervention Visits ²		✓	✓	✓	✓	✓	✓	✓	✓	✓	✓	
Assess adverse events	✓	✓	✓	✓	✓	✓	✓	✓	✓	✓	✓	
Tissue collection for biomarkers												✓

Footnotes:

1. Fasting serum biomarkers/bioassays to be studied are IGF-1 and IGFBP-1 and the ex-vivo mitogenic and apoptotic activity of subject serum on LNCaP cells. Additional fasting serum studies will be insulin, PSA, and lipids.
2. The No Weight Loss Group has the same Baseline Visit procedures and Final Visit procedures (within 3-days prior to surgery) as the Weight Loss Group: Dexa Scan, fasting serum biomarkers, anthropometrics, and a 3-Day Food Diary.
3. At week 9 or Final Waist/Hip Measurement will be at the Final Visit Prior to Surgery.

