Control – No Weight Loss Intervention Group: After randomization to the control group, these men will proceed with radical prostatectomy as scheduled. They will have one additional visit to the VA CRC within 3 days prior to radical prostatectomy for measurement of weight, height, and waist to hip ratio, fasting blood will be collected for biomarkers and a DEXA Scan. During the week prior to the radical prostatectomy a 3-Day Food Record will be completed as well. We are doing this second visit in the control group to monitor for possible weight loss that these subjects may initiate on their own, although we do not anticipate this occurring to any significant degree. Subjects in the Control group will be given the phone number of the study coordinator to schedule their optional 5-8-week weight loss program after they have recovered from their surgery. This optional weight loss program is given as an incentive for their participation in the trial.

Weight Loss Intervention Group: Subjects randomized to the Weight Loss Group will receive an appointment to the VA CRC to meet with the research study coordinator and the study dietician to initiate the weight loss intervention. Subjects will receive one of two standard structured energy-restricted meal plans (1200, 1500, 1800 Kcal/day) using meal replacements and portion-controlled foods. Prescribed plans will be based upon resting energy expenditure and lean body mass as determined by DEXA scanning. The goal of the meal plan is to provide a total calorie intake incorporating 500-800 Calorie deficits per day. Since men will be provided with exercise regimens as well, they should experience a 1 to 2 pound weight loss per week during the weight loss intervention. Based on our experience in prior trials, we anticipate subjects will lose 4-6% of their body weight over 5-8-weeks as a result of the weight loss intervention.

Subjects will have weekly visits with the study dietician until the time of the radical prostatectomy. [name] or her associates will oversee each of these visits with the study dietician. The subject will receive instruction on recipes, ideas and places for food shopping, education on healthy food preparation, and preparation of meal replacements. Recommended diets will

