contain 20-25% energy from fat, 15-20% from protein and 50-65% from carbohydrates largely from fruits and vegetables with some whole grains. Fiber recommendations will be a total of 25 grams/day from fruits, vegetables, legumes, and high fiber cereals.

Subjects will be counseled by [name] or her associates on performing 1 hr of exercise/day including aerobic, resistance, and flexibility activities. As an exercise incentive, subjects will be given a pedometer and exercise an log (Appendix 3) to complete and results will be reviewed with the dietitian at each visit. Subjects will be weighed at each visit and waist to hip ratio will be measured at the Screening or Baseline, Weeks 2, 4 and 9. Following the 4-9-week weight loss intervention and within 3 days prior to radical prostatectomy, weight and waist to hip ratio will again be measured, fasting serum will be collected for biomarkers, and a DEXA Scan will be performed to assess the change in body fat and lean body mass as a result of the intervention. In addition, during this week subjects will also complete a 3-day Food Diary to assess dietary and caloric intake to bring with them for their final study visit prior to surgery.

At each study visit, we will go over concomitant medications, adverse events and we will assess subjects for fatigue as well as the ability to perform their usual daily tasks (functional ability). If subjects have significant loss of strength or daily function, we will take them off protocol and have them re-evaluated in the preoperative clearance clinic at the West Los Angeles VA to make sure they can safely undergo radical prostatectomy.

Post-Prostatectomy Follow-up: Subjects in the Weight Loss Group will have scheduled visits at 3 months and 9 months post-op to assess for adverse events, and to measure body weight to determine if subjects maintain the weight loss achieved during the pre-operative intervention. If they are unable to come to the VA, this visit can take place over the phone. This will be the same for the Control subjects.

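### Before surgery, adverse events and medications are checked repeatedly in the weight-loss arm but at most once, and possibly not at all, in the control arm

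*Combined protocol and SAP*

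**What the plan says.** All of the relevant text is in section 3 (Work Proposed) of the combined protocol and SAP.

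**Weight-loss arm.** The Weight Loss Intervention Group text states: "Subjects will have weekly visits with the study dietician until the time of the radical prostatectomy". Later in the same text comes: "At each study visit, we will go over concomitant medications, adverse events and we will assess subjects for fatigue", together with a check on daily functioning. In the Clinical Trial Flow Chart the row "Assess adverse events" is ticked at V1 to V11. The concomitant-medication row, as extracted, is ticked at V1 and V3 to V11.

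**Control arm.** The control-group text states: "They will have one additional visit to the VA CRC within 3 days prior to radical prostatectomy". The content it names is body measurements, fasting blood and a DEXA scan, with a food record in the preceding week. It gives the reason for the visit: "We are doing this second visit in the control group to monitor for possible weight loss that these subjects may initiate on their own". Safety is not mentioned.

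**Flow chart footnote 2.** It opens "The No Weight Loss Group has the same Baseline Visit procedures and Final Visit procedures (within 3-days prior to surgery") and continues "as the Weight Loss Group: Dexa Scan, fasting serum biomarkers, anthropometrics, and a 3-Day Food Diary". Neither adverse events nor medications are named.

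**After surgery.** Post-Prostatectomy Follow-up schedules adverse-event assessment at 3 and 9 months, on the same terms in both arms.

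**Analysis.** The Statistical Analysis section names no harms outcome and describes no adverse-event analysis.

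**The concern.** The number of events recorded depends on how often, and how, people are asked. If one arm is asked weekly and the other once or never, the first arm will tend to show more events even when the true rates are equal. Ordinary pre-operative complaints would then look like effects of the intervention, and real effects could not be separated from background.

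The window matters. The weeks before surgery are the only period in which the intervention is set against men who have not been offered it. Afterwards both arms have had major surgery, and controls may take up the program once they recover. Fatigue and loss of function are the harms the plan specifically watches for. Without control data there is no background rate against which to read them.

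The same gap affects medications and supplements. The notes to the eligibility criteria say that lycopene has been shown to affect apoptosis in prostate cancer tissue, and that changes in insulin may affect IGF-1 and IGFBP-1. The primary outcome is the apoptotic index at prostatectomy. The undertaking to stop supplements is tied to the start of the dietary intervention, which controls do not begin before surgery. If nobody asks, new use in controls of an agent the plan itself regards as relevant could go unrecorded.

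**Working it through.** The documents give no figure for harms, so there is none to reproduce. The check is a count of scheduled assessments between randomization and surgery.

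**Inputs**
- Randomization falls within 3 days of the first visit (Study Procedures), so V1 is before it and V2 after it.
- The intervention lasts 4 to 9 weeks. V2 is the first intervention visit, V6 is week 4 and V11 is week 9 (flow chart).
- Controls have one visit after randomization and before surgery (control-group text). Their baseline DEXA and serum are taken at V1, before randomization.

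**Adverse-event checks per man**
- Weight loss, 4 weeks: V2 to V6 = 1 + 4 = 5.
- Weight loss, 9 weeks: V2 to V11 = 1 + 9 = 10.
- Leaving out V2, when the intervention is only starting: 4 to 9.
- Control: 0 on the two lists as written, or 1 if the opening of footnote 2 or the sentence about each study visit is taken to include controls.

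**Medication checks per man** (V2 not ticked, as extracted)
- Weight loss: 4 to 9.
- Control: 0 or 1.

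**Across the planned sample, with full attendance**
- Weight loss: 35 × 5 = 175 to 35 × 10 = 350 adverse-event checks.
- Control: 30 × 0 = 0 or 30 × 1 = 30.

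**After surgery:** 2 checks (3 and 9 months) in each arm, so no imbalance.

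**What the imbalance could do (illustration only; none of these rates is in the documents).** Assume the same weekly event risk p in both arms, and that each check picks up only the past week. The share of weight-loss men with any recorded event over L weekly checks is 1 − (1 − p)^L. With one control check it is p; with none it is 0.

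| p | Weight loss, L = 4 | Weight loss, L = 9 | Control, one check | Control, none |
|---|---|---|---|---|
| 5% | 18.5% | 37.0% | 5% | 0% |
| 10% | 34.4% | 61.3% | 10% | 0% |

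At the other extreme, with perfect recall over an equally long interval, one control check would record the same share as weekly checks and the gap would vanish. The direction is therefore clear, toward more recorded events in the weight-loss arm, but the documents do not fix its size.

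**The case against.** The strongest reply is that the omission may be only apparent. Footnote 2 says the arms share the same baseline and final procedures, and its list describes both visits and both arms. Read as exhaustive, it would also remove adverse-event review from the weight-loss arm's own final visit, and consent and history from baseline. It may simply highlight the study measurements. The sentence on reviewing adverse events and medications at each study visit is not limited to one arm in its wording, although it stands in the weight-loss text. This part of the objection holds: a reader might infer that controls are certainly never asked, and the documents do not establish that. Hence the count of 0 or 1. But the control-group text gives its own list and a purpose unrelated to safety, and even one check stands against 5 to 10.

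A second reply is that weekly questioning protects participants who are dieting and exercising, follows naturally from weekly dietitian visits, and feeds no planned between-arm analysis. That is fair, and it limits the severity. It does not make the pre-surgical records comparable if anyone later tabulates them by arm.

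Third, weight, PSA and testosterone are measured in controls before surgery, and nothing suggests that they would start the excluded drugs. These are indirect signals. They do not record medication use, and they would not reveal lycopene or other supplements.

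**Conclusion.** Pre-surgical ascertainment is unequal: 5 to 10 scheduled adverse-event checks against 0 or at most 1, and 4 to 9 medication checks against 0 or 1. The counts rest on the flow chart as extracted and on full attendance. Any between-arm comparison of pre-surgical harms, or of new medication or supplement use before prostatectomy, is open to ascertainment bias.

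Three stronger conclusions might be inferred, and the documents do not support them.
- **That the trial can give no unbiased comparison of harms at all.** Post-operative assessment follows the same schedule in both arms, so the problem is confined to the weeks before surgery.
- **That the primary result is biased by this.** Tissue is scored blind, and adverse-event and medication records do not enter the primary test. The loss is the ability to see and describe differential use of relevant agents.
- **That the bias has a known size.** Any percentage depends on assumed event rates and recall.

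The severity is modest: no stated endpoint, planned analysis or sample-size figure changes. The correction is still worthwhile because it is cheap and this window cannot be reconstructed later.

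**What to change.** 1. In the control-group text and in flow chart footnote 2, list adverse events, concomitant medications and supplements, and the fatigue and function question as part of the control final visit.
2. At the final visit in both arms, use one identical form that asks about the whole period since randomization.
3. State in the Statistical Analysis section that any between-arm comparison of pre-surgical events or medication use rests on that common record, and that the additional weekly reports from the weight-loss arm are shown separately as descriptive.
4. Report the time from randomization to surgery by arm beside that comparison. The control-group text fixes no interval, and an identical question does not equalize time at risk.

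The weekly safety review in the weight-loss arm need not change.

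The cost is a few minutes at a visit that already takes place, one shared form and a few sentences of text. The drawback is recall: controls must look back over the whole interval without weekly prompts, while weight-loss participants will have been prompted. The common question reduces the imbalance but may not remove it entirely, and the report should say so.

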3. WORK PROPOSED

Overview: The study design for the present proposal is illustrated below. To obtain adequate power to detect a difference in prostate tumor apoptosis between the groups, the trial will require 30 patients per group. Based on our prior experience with the weight loss intervention we will be using in this trial, we are assuming a 15% dropout rate in the Weight Loss Group. Therefore, we are adding an additional 5 subjects to the Weight Loss Group to bring the total in this group to 35 and the total in the overall trial to 65.

Screening and Recruitment of Subjects - Minority Participation: Subjects will be recruited for the present trial from the VA Medical Center, Greater Los Angeles Health Care System. [name] conducts the urologic oncology clinic at the VA in which 130 new prostate cancer cases are diagnosed per year. Subjects with a new diagnosis of prostate cancer at the VA are offered standard therapies as well as the opportunity to participate in clinical trials. Subjects expressing interest in the weight loss trial will be given the consent form to review and the phone number of [name] research coordinator. Given the high prevalence of overweight and obese subjects (up to 70 % at our VA¹⁰), and given the high number of radical prostatectomy procedures performed at our VA (40/year), we anticipate no problem meeting our

recruitment goal of 65 subjects over 5-years. As well, given that 40-50% of men that undergo radical prostatectomy at the VA are AAM, we anticipate 40-50% of men in our clinical trials will be AAM.⁶² This is extremely important given the increased risk of obesity in AAM and the undue burden of increased morbidity and mortality of prostate cancer in AAM. For men randomized to the weight loss intervention group, the 4-9 week delay in radical prostatectomy has been shown not to increase the risk of biochemical recurrence.⁶³ However, we will not enter patients in this trial with a high risk of having advanced disease (Gleason Grade > 4+4) to avoid the potential risk (albeit extremely low) for progression during the weight loss intervention.

Inclusion Criteria:

1. Subject is overweight or obese (BMI > 25 kg/m²)
2. Patient with pathologically confirmed adenocarcinoma of the prostate and has elected to undergo radical prostatectomy
3. Able to adhere to physical activity intervention (able to walk for 10 minutes without rest)

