Study Procedures: Subjects will have their first study visit at the VA Greater Los Angeles Healthcare System Clinical Research Center (CRC) which will include subject consent and review of the entry criteria. Once consent is obtained, a medical history and physical exam will be performed including height, weight, and measurement of waist to hip ratio (anthropometrics). The urologist's DRE and clinical stage will be recorded from the subject's urology note, and prostate needle biopsy pathology including Gleason grade and percent of cores with cancer will be recorded. A fasting serum specimen will be collected for biomarker studies. A DEXA scan will be performed (to determine lean body mass to calculate caloric intake for the weight loss program) and to determine percent body fat. The Subject will then return home and during the next week will keep a 3-Day Food Diary (Appendix 2). Subject's will be randomized within 3-days of their initial visit and contacted at home with the results of the randomization.

Randomization: If a subject meets all eligibility criteria, the following steps will occur:

1. The study coordinator will FAX the subject's initials, study ID, and date of visit to the junior statistician (to be named).
2. Within 24 hours the statistician will inform the research coordinator of the randomization result (weight loss vs. No Weight Loss Group) and date of randomization. The research coordinator will inform the study subject of the results and schedule subsequent study visits.
3. The randomization will use a permuted block design with 5 blocks of size 13 (7 weight-loss and 6 no weight-loss).

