Immunostaining and Interpretation: Immunostaining of paraffin embedded pretreatment prostate needle biopsy specimens and malignant tissue from radical prostatectomy specimens will be performed using ki67 monoclonal antibodies (DAKO) and a TUNEL assay (BioVision). The cancer tissue with the highest Gleason grade will be analyzed in a blinded fashion by counting 300 cancer cells per slide. Our main objective (Objective 1 of this proposal) will be to compare the percent of cells staining positive for ki67 and TUNEL between the Control Group-No Weight Loss and Weight Loss Group (controlling for Gleason grade). We will also compare the percent of cells staining for ki67 and TUNEL in the prostate needle biopsy specimen relative to the prostatectomy tissue (also matching for Gleason grade). In addition, we will perform correlation analysis to determine if weight loss correlates with proliferation and apoptosis. We hypothesize that with increasing weight loss there will be decreased ki67 staining and an increasing percentage of cells with TUNEL staining. To further evaluate the effect of weight-loss on prostate tumor staining of the IGF signaling cascade we will analyze immunostaining of phospho-IGF-1R (using a Cell Signaling antibody) and phospho-Akt (Cell Signaling). We will also evaluate for earlier stages of apoptosis as measured by activated caspase-3 (Oncogene). If we detect changes in apoptosis, we will also stain for BAX and BCL2 using antibodies from R&D. If we detect changes in proliferation as measured by ki67 staining, we will also stain for Mcm-2 (which has been shown to be a prognostically important prostate cancer proliferation marker) using antibodies from R&D.⁶⁶

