Statistical Design: The statistical design of this study is a randomized repeated measures utilizing random mixed block sizes known only to the statistician constructing the randomization list to assign subjects to two study arms in a ratio of 7:6, weight loss to no weight loss.

Sample Size Determination: An evaluable sample of at least 60 subjects (no weight loss=30, weight loss=30) is expected to provide 80% power to detect an effect size of 0.74 using a two group t-test with a 0.050 two-sided significance when comparing the apoptotic index (primary outcome variable) in the radical prostatectomy malignant epithelium between the weight loss and no Weight Loss Group. The apoptotic index will be measured in the malignant epithelium with the highest Gleason grade. To account for a post-randomization attrition rate of up to 15% in the Weight Loss Group, a total of 35 subjects will be randomized to the Weight Loss Group, thus bringing the total sample size to 65 subjects. Kim et al. observed an effect size of 1.74 on apoptotic index using a nutritional intervention in a similar study.⁶⁴

Data Analysis: Data analyses will be performed on randomized subjects who complete the study. All parameters measured will be summarized descriptively. The number of subjects, mean, standard error of the mean, median and min-max values will be presented for continuous parameters and the number and percentage of subjects in each category will be presented for categorical parameters. No imputation of missing data is planned. Demographic and baseline characteristics will be summarized using descriptive statistics overall and by treatment group to assess baseline comparability. Treatment groups will be compared using the appropriate nonparametric tests for categorical parameters and analysis of variance models for continuous parameters.

Primary Outcome Variable: The primary outcome variable is apoptotic index of the highest Gleason grade malignant epithelium in the radical prostatectomy specimen. The primary objective is to compare the mean apoptotic index between the Weight Loss Group and the Control Group-No Weight Loss. The two independent sample t-test will be used to compare the index between the groups. If the index is non-normally distributed we will use the Wilcoxon rank sum test. Next, linear regression models will be constructed to test whether the treatment effect

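### Randomization step 3 prints five fixed blocks of 13, while the Statistical Design paragraph says block sizes are random, mixed and secret; both cannot be true

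*Combined protocol and SAP*

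**What the plan says.** Section 3 (Work Proposed), Randomization, step 3: "The randomization will use a permuted block design with 5 blocks of size 13 (7 weight-loss and 6 no weight-loss". This fixes the number of blocks, their common size and their composition.

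Section 3, Statistical Analysis, Statistical Design: the list is built "utilizing random mixed block sizes known only to the statistician constructing the randomization list", and is used "to assign subjects to two study arms in a ratio of 7:6, weight loss to no weight loss".

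The Overview gives the totals. Five extra men are added to the weight-loss arm "to bring the total in this group to 35 and the total in the overall trial to 65".

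Two further statements set the context. Recruitment is at one centre: "Subjects will be recruited for the present trial from the VA Medical Center, Greater Los Angeles Health Care System". Under Randomization, step 2, "Within 24 hours the statistician will inform the research coordinator of the randomization result", and the coordinator then tells the subject.

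No text reconciles the two descriptions or says which one governs.

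**The concern.** The two descriptions disagree on two properties of the list: whether block size is constant or varies, and whether it is disclosed or secret. A reader cannot tell which list was, or will be, built. Any report of the method will contradict one of the two paragraphs.

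The second property matters for allocation concealment. The intervention is open to the coordinator and the subject, and one site sees every result. Keeping block sizes secret is the safeguard that the Statistical Design paragraph claims. The scheme printed in step 3 does not have it, because anyone who holds the protocol knows where each block ends. Someone who also kept count could know some assignments before they were requested. Some entry criteria call for judgement (ability to follow the activity programme, significant co-morbidities), so foreknowledge could in principle influence who is approached or enrolled.

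**Working it through.** **1. Reproduce the plan's totals.** Inputs are from step 3.
- 5 × 13 = 65 assignments
- 5 × 7 = 35 weight loss
- 5 × 6 = 30 no weight loss

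These match the Overview and the Sample Size Determination paragraph. The ratio and the totals are therefore not in dispute.

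**2. Can both descriptions hold?**
- *Constant or mixed.* Five blocks of 13 exhaust the 65 assignments, so no block of another size remains.
- *Could step 3 be one instance of a mixed list?* No: five equal blocks are not mixed sizes. Suppose also that every block must hold 7:6 exactly. Then 7/13 of its size must be a whole number, so the only sizes up to 65 are 13, 26, 39, 52 and 65. Five such blocks reach 65 only if all are 13, so a mixed list has at most four blocks (for example 13 + 13 + 13 + 26).
- *Could step 3 be an example?* It is worded as what will be done.
- *Disclosed or secret.* Number, size and composition are all printed.

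**3. What the printed scheme gives away.** Assume an observer who knows the block size and has tracked every earlier assignment. Once one arm is used up within a block, the rest of that block is certain. The expected number of certain assignments in a block with *a* and *b* men (*n* = *a* + *b*) is the sum over *k* of

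[C(n−k, a−k) + C(n−k, b−k)] / C(n, a)

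which adds up the chances that the last *k* assignments are all to one arm. With a = 7, b = 6 and C(13, 7) = 1716:

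| k | numerator | probability |
|---|---|---|
| 1 | 924 + 792 = 1716 | 1.0000 |
| 2 | 462 + 330 = 792 | 0.4615 |
| 3 | 210 + 120 = 330 | 0.1923 |
| 4 | 84 + 36 = 120 | 0.0699 |
| 5 | 28 + 8 = 36 | 0.0210 |
| 6 | 7 + 1 = 8 | 0.0047 |
| 7 | 1 + 0 = 1 | 0.0006 |

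The sum is 3003/1716 = 1.75 per block. Over five blocks, 5 × 1.75 = 8.75, and 8.75/65 = 13.5%. The last assignment of each block (5 of 65) is always among them.

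**4. How much of that comes from knowing the size?** With the same five blocks but an observer who knows only the 35:30 totals, only the final run of the whole list is certain. That is 1.75 on average. Knowing the size accounts for 8.75 − 1.75 = 7.0 assignments.

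**The case against.** The strongest reply is that this is a wording conflict with little practical consequence. Much of that stands.

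- Five blocks of 13 is a legitimate permuted-block design that delivers exactly 35:30. The defect is the contradiction, not the choice of blocks.
- The route to misuse is narrow. Each assignment comes from a statistician, and only after eligibility is established: "If a subject meets all eligibility criteria, the following steps will occur". Decisions to approach a patient and to obtain consent come earlier, however, so the route is not fully closed.
- Biased reading of the tissue outcome is guarded against separately: "The cancer tissue with the highest Gleason grade will be analyzed in a blinded fashion by counting 300 cancer cells per slide".
- The 8.75 figure needs an observer who knows the size and tracks every result without error. The document gives no sign of one.

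A reader might also infer that printing the size makes assignments easier to guess overall. It does not. With the size known, the best guess is right G(7,6) = 8.387 times per block, from G(a,b) = max(a,b)/(a+b) + [a·G(a−1,b) + b·G(a,b−1)]/(a+b). Over five blocks that is 41.93 of 65 (64.5%). An observer of the same blocks who knows only the 7:6 ratio, and guesses the arm that is behind, scores the same 64.5%. What printing the size adds is certainty about some assignments, not better guessing on average.

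The contradiction survives these points. Two current statements of method conflict, and one claims a concealment property that the other lacks.

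**Conclusion.** The inconsistency is real and should be corrected. Step 3 and the Statistical Design paragraph cannot both describe the list, and nothing in the document decides between them.

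The size, if the printed scheme is used, is an average of 8.75 of 65 assignments (13.5%) certain in advance. This rests on two assumptions: someone at the site knows the block size, and that person tracks every result. The second is possible because the coordinator receives each one.

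Two stronger conclusions are tempting but unsupported. A reader might infer that allocation was foreseen or that selection bias occurred, but nothing in the document shows either. A reader might also infer that the sample size or the test is affected. It is not: the totals of 35 and 30, the 7:6 ratio, the 80% power and the two-sided 0.05 level are the same under either scheme.

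**What to change.** State one scheme in both places and report the scheme actually used. The document does not give recruitment status, so the edit depends on it.

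- **No list in use yet.** Keep the Statistical Design paragraph. Delete the number, size and composition of blocks from step 3 and leave only the 7:6 ratio. The statistician generates a mixed-size list that ends at 35:30, chooses the sizes, and keeps them unpublished.
- **A mixed-size list already in use.** Correct step 3 only.
- **Blocks of 13 in use, or enrolment completed on them.** Correct the Statistical Design paragraph by removing the statements that sizes are random and mixed and that only the statistician knows them.

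In the last two cases the cost is a wording correction, and no running list is altered. In the first it is one protocol sentence and one list, with arm totals, sample size and power unchanged.

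One design point belongs to the statistician. The Statistical Design paragraph gives 7:6 for assignment to the arms and does not require it within each block. If it is required within each block, sizes must be multiples of 13, and larger blocks allow slightly more temporary imbalance. The mid-block standard deviation of the weight-loss count, √[n(7/13)(6/13)(N−n)/(N−1)], is 0.93 man for N = 13 (n = 6), 1.30 for N = 26 (n = 13), 1.58 for N = 39 (n = 19) and 1.81 for N = 52 (n = 26). The plan expects 65 men over 5 years, or 13 a year if accrual is even. A block of 52 would then span about four years (52/13) and give up much of the balance over time that blocking provides, so very large blocks are unattractive.
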